### 10.4.2 Safety Endpoints

The primary safety endpoint is the number/proportion of participants with DLTs (including participants with Grade 4 ANC decrease), and AEs, and who discontinue study treatment due to AEs. In addition, safety and tolerability will be assessed by clinical review of all relevant parameters including adverse events (AEs), laboratory tests, and vital signs.

A description of safety measures is provided in Section 9.5 - Safety.

### 10.5 Analysis Populations

### 10.5.1 Efficacy Analysis Populations

The Full Analysis Set (FAS) population will be used for the analyses of efficacy data in this study. It consists of all participants with a baseline scan that demonstrated measurable disease by the investigator's assessment, and who were administered at least 1 dose of study medicine.

### **10.5.2** Safety Analysis Populations

The All-Subjects-as-Treated (ASaT) population will be used for the analysis of safety data in this study. The ASaT population consists of all participants who received at least 1 dose of study treatment.

The DLT evaluable population includes ASaT participants that meet the criteria for DLT evaluability (e.g., finished Cycle 1 without a DLT or experienced a DLT in Cycle 1). See Section 5.1.3 for details.

At least 1 laboratory or vital sign measurement obtained subsequent to at least 1 dose of study treatment is required for inclusion in the analysis of each specific parameter. To assess change from baseline, a baseline measurement is also required.

### 10.5.3 Pharmacokinetic Analysis Populations

The Per-Protocol (PP) population will be used for the analysis of PK and PD data in this study. The PP population consists of the subset of participants who complied with the protocol sufficiently to ensure that their data will be likely to exhibit the effects of treatment, according to the underlying scientific model. Compliance includes such considerations as exposure to treatment, availability of measurements, and the absence of major protocol violations. Any participants or data values excluded from the analyses will be identified. along with the reasons for exclusion, in the CSR. At the end of the study, all participants who were compliant with the study procedures and have available data from at least 1 treatment will be included in the PP analysis dataset.

#### 10.6 Statistical Methods

07WYDZ

04W5XD

This section describes the statistical methods that address the primary objectives. Methods related to secondary and exploratory objectives as well as the comparison between the t2arms will be described in the sSAP. The final analyses will be performed using data from both Stage 1 and Stage 2.

MK-7123-034-01 Final Protocol 22-Mar-2018 Confidential

91

**Product:** MK-7123 SCH 527123 **Protocol/Amendment No.:** 034-01

### 10.6.1 Statistical Methods for Efficacy Analysis

ORR will be estimated using an exact method based on the binomial distribution together with its 95% confidence interval (Clopper-Pearson interval).

Methods for the secondary and exploratory efficacy analyses as well as the comparison between the two arms will be documented in the sSAP.

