The overall design is an adaptive 2-stage design. In each arm, up to 30 participants will be enrolled in the first stage, and up to 30 participants in the second stage. In the first stage, 30 participants (with 10 per tumor type) will be enrolled in each arm (dose level). When all participants in a given arm with a given tumor type complete the first on-treatment scan at 9 weeks or when clinically indicated (see Section 9.2.1.2), a futility analysis will be conducted to determine whether that tumor type and arm will progress to Stage 2. If a tumor type passes the futility analysis (see Section 5.1.4) in Stage 1, at least 10 participants will be enrolled with that tumor type in the second stage.

Initial enrollment in each dose arm will be staggered. The first 3 participants in dose Arm A or dose Arm B will be enrolled no more frequently than 1 participant per week, to allow for peripheral neutrophil assessment between participants. Peripheral neutrophil assessment (ANC) will occur at baseline, Day 3, and Day 8 during the first cycle for all participants. Decreased ANC counts typically return to normal in 48-96 hours following dosing cessation. Standard support for oncology patients with low ANC will be considered as appropriate. See dose reduction algorithm (Section 7.2.1) for more information.

Specific procedures to be performed during the study, as well as their prescribed times and associated visit windows, are outlined in the Study SoA - Section 2. Details of each procedure are provided in Section 9 – Study Assessments and Procedures.

04W5XD

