#### **Futility Analysis** 5.1.4

An interim futility analysis for efficacy will be performed after the first 10 participants for each tumor type have at least 1 post-baseline scan assessment in each dose arm in Stage 1. If one or more responses (confirmed or unconfirmed) are observed for a tumor type in an arm (i.e.  $\geq$ 10% response rate), this tumor type may be expanded to enroll at least additional 10 participants in Stage 2, for a maximum enrollment of 60 participants in this arm across 3 tumor types. Otherwise, this tumor type may be stopped early for futility.

If the decision is made to expand a tumor type in dose Arm A to Stage 2, this tumor type in dose Arm B may be expanded to Stage 2 as well, irrespective of the number of responses as long as it has passed the safety evaluation. While the decision rule is mainly based on confirmed and unconfirmed responses, the totality of data will also be taken into account.

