#### 10.4 Analysis Endpoints

### 10.4.1 Efficacy/Pharmacokinetics/Pharmacodynamic Endpoints

ORR as assessed by the investigator based on RECIST 1.1 is the primary endpoint. ORR as assessed by the investigator based on iRECIST, PFS as assessed by investigator based on RECIST 1.1 and iRECIST and OS are the secondary endpoints in this study. A description of efficacy measures is provided in Section 9.2 – Efficacy Assessments.

Objective Response rate (ORR) is defined as the proportion of participants who achieve a confirmed complete response (CR) or partial response (PR).

Progression-free Survival (PFS) is defined as the time from the first dose of study medication to the first documented disease progression or death due to any cause, whichever occurs first.

Overall survival (OS) is defined as the time from the first dose of study medication to death due to any cause.

Pharmacokinetic endpoints include serum concentrations of navarixin and pembrolizumab, as well as derived PK parameters.

Pharmacodynamic endpoint includes ANC.

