### 10.9 Sample Size and Power Calculations

For the planning purpose, it is assumed that true objective response rates of <1% for MSS CRC and 5% for PDL1-refractory NCSLC and advanced prostate are not considered clinically meaningful, whereas true objective response rates of 16% for MSS CRC and 20% for PDL1-refractory NCSLC and advanced prostate or higher are. With 20 participants in each tumor type of each arm under the 2-stage adaptive design, the probability that the objective response rate of each tumor type is claimed clinical meaningful is less than 8% when the true response rate is not clinically meaningful and more than 75% when the true response rate is clinically meaningful. The total sample size is 60 participants per arm (20 per each tumor type in an arm). No formal hypothesis testing will be conducted. Table 8 provides the probability that the objective response rate of each tumor type is claimed clinical meaningful under different true ORR. Table 9 shows the hypothetical ORR estimates and the CI (Clopper-Pearson interval) based on sample size of 20 per tumor type. Due to a small sample size, even an observed response rate as high as 30% (6 out of 20) could be coming from a true signal as low as 14%. A higher observed responses rate such as 8 out of 20 would be more indicative of a true response rate above 20%.

Probability That ORR is Claimed as Clinical Interest With 20 Participants in Each Table 8 Tumor Type of Each Arm

Tumor Type	ORR as clinical meaningful	True ORR	Minimum Responses that ORR is claimed as clinical meaningful	Probability that ORR is claimed as clinical meaningful
CRC	16%	1%	2	1%
		16%	2	77%
NSCLC,				
Prostate	20%	5%	3	7%
		20%	3	76%

The CI of the True ORR Under Different Hypothetical Number of Observed Response Scenarios With 20 Participants in Each Tumor Type of Each Arm

Hypothetical number of responses (CR or PR)	ORR	90% CI of ORR	80% CI of ORR
2	10%	(1.8%, 28.3%)	(2.7%, 24.5%)
3	15%	(4.2%, 34.4%)	(5.6%, 30.4%)
4	20%	(7.1%, 40.1%)	(9.0%, 36.1%)
5	25%	(10.4%, 45.6%)	(12.7%, 41.5%)
6	30%	(14.0%, 50.8%)	(16.6%, 46.7%)
7	35%	(17.7%, 55.8%)	(20.7%, 51.8%)
8	40%	(21.7%, 60.6%)	(24.9%, 56.7%)

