## 10.10 Subgroup Analyses

Efficacy endpoints will be analyzed by arm for each tumor type. Additional subgroup analyses (e.g., by age, gender, and race) may be conducted as needed and will be documented in the sSAP.

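### Section 10.6.1 pools both stages without allowing for the Stage 1 futility rule, so the ORR of cells that pass it is biased upward, mainly at low true rates; show a Stage 2-only ORR beside it

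*Combined protocol and SAP*

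**What the plan says.** Section 10.6.1 gives the whole method for the primary efficacy endpoint: "ORR will be estimated using an exact method based on the binomial distribution together with its 95% confidence interval (Clopper-Pearson interval". Section 10.6 adds: "The final analyses will be performed using data from both Stage 1 and Stage 2". Section 10.10 sets the unit of reporting: "Efficacy endpoints will be analyzed by arm for each tumor type".

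Section 5.1.4 sets the route into Stage 2. The trigger is "If one or more responses (confirmed or unconfirmed) are observed for a tumor type in an arm", and then "this tumor type may be expanded to enroll at least additional 10 participants in Stage 2". The same section softens the rule in two ways. The totality of the data also counts, and a tumor type in Arm B may expand once it expands in Arm A, whatever its own response count.

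The futility rule counts unconfirmed responses, but the final endpoint does not (Section 10.4.1): "Objective Response rate (ORR) is defined as the proportion of participants who achieve a confirmed complete response (CR) or partial response (PR".

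Section 10 names no estimate that allows for the futility rule and no Stage 2-only estimate. The supplemental SAP is reserved for secondary and exploratory methods and the comparison of arms, so the primary ORR is not deferred to it.

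**The concern.** A cell that continues has normally been chosen because its first 10 participants did well enough. Those 10 are then added to the Stage 2 participants, and the total is treated as an unselected binomial sample. Part of the result is the selection itself.

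The expanded cells are the ones the sponsor will look at when choosing a tumor type and dose to take forward, and Section 5.4.1.1 names ORR as the basis for decisions. The selection effect is largest where the true rate is lowest, so it makes inactive cells look nearer to active ones.

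**Working it through.** **Inputs**
- Stage 1 size per cell is 10 (Section 5.1): "30 participants (with 10 per tumor type) will be enrolled in each arm (dose level".
- Planned total per cell is 20 (Section 10.9): "With 20 participants in each tumor type of each arm under the 2-stage adaptive design". Stage 2 is therefore 10 for planning, although Section 5.1.4 makes 10 a minimum.
- Futility rule: at least 1 response in 10.
- Rates in Table 8: 1% and 16% for MSS CRC, 5% and 20% for NSCLC and prostate. Claim thresholds are 2/20 and 3/20.

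**Step 1. Reproduce the plan's figures.** The chance of passing is 1 − (1 − p)^10, which gives 82.5% at 16% and 89.3% at 20% (Section 10.7 states 82% and 89%). For Table 8, sum P(X1 = x) · P(X2 ≥ r − x) over x = 1 to 10, with X1 and X2 each Bin(10, p).

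| True ORR, threshold r | Table 8 | With futility rule | Ignoring it |
|---|---|---|---|
| 1%, r = 2 | 1% | 1.3% | 1.7% |
| 16%, r = 2 | 77% | 76.7% | 85.3% |
| 5%, r = 3 | 7% | 6.9% | 7.5% |
| 20%, r = 3 | 76% | 75.9% | 79.4% |

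The 77% and 76% fit only when the rule is included. The plan allows for it in the decision probabilities but not in the estimate.

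**Step 2. Expected pooled ORR given a pass.** This is {10p / [1 − (1 − p)^10] + 10p} / 20. At p = 5% the chance of passing is 40.1%, the expected Stage 1 count given a pass is 0.5 / 0.4013 = 1.246, and (1.246 + 0.5) / 20 = 8.7%. The all-cells figure counts stopped cells as 0/10, so it is the chance of passing times the conditional value: 0.4013 × 8.73% = 3.5%.

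| True ORR | Passes | Pooled ORR given a pass | Pooled ORR, all cells | 95% CI coverage given a pass |
|---|---|---|---|---|
| 1% | 9.6% | 5.7% | 0.55% | 86.4% |
| 5% | 40.1% | 8.7% | 3.5% | 96.2% |
| 10% | 65.1% | 12.7% | 8.3% | 98.3% |
| 16% | 82.5% | 17.7% | 14.6% | 98.9% |
| 20% | 89.3% | 21.2% | 18.9% | 98.9% |

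**Step 3. Vary the assumptions at a true confirmed rate of 5%.** The ranges are mine, since the documents give none.
- *Any-response rate q at the futility look.* Replace the pass probability by 1 − (1 − q)^10. For q = 6.25%, 7.5% and 10% the result is 7.8%, 7.1% and 6.3%.
- *Stage 2 of 15 or 20 participants.* (1.246 + 0.75) / 25 = 8.0%, and (1.246 + 1.0) / 30 = 7.5%.
- *A fraction f of zero-response cells expanded anyway.* Replace the pass probability by 0.4013 + 0.5987f. For f = 25% and 50% the result is 7.0% and 6.1%.
- *Arm B expanded whenever either arm passes, both at 5%.* The expansion probability is 1 − 0.5987² = 0.6415, which gives (0.5 / 0.6415 + 0.5) / 20 = 6.4%.

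**Step 4. Interval coverage given a pass.** At a true 1%, the lower limit for 2/20 is 1.2%, so any total of 2 or more excludes the truth. That has probability 0.0130 / 0.0956 = 13.6%, so coverage is 86.4%. At 3% coverage is 92.8%. It holds at 5%, 10%, 16% and 20%. Exact coverage is saw-toothed: just below 5.7%, the lower limit for 4/20, it dips to 94.7%, which is immaterial.

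**The case against.** Four points weigh on the other side.

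1. *The decision rule is already sound.* The claim rests on a count of 2 or 3 in 20, and Table 8 allows for the futility rule. No formal test is planned. A reader might infer that the stated decision probabilities are wrong; Step 1 shows that they are not. This stands in full, so the point concerns the reported estimate only.
2. *The bias is small where the drug works:* +1.7 points at 16% and +1.2 at 20%. This stands.
3. *Over all cells the pooled estimate is too low, not too high* (3.5% at a true 5%, 18.9% at a true 20%). This stands. The upward bias belongs only to cells that pass. Those are, however, the cells whose results will be read as promising.
4. *A Stage 2-only estimate is imprecise.* Given a pass, its root mean squared error exceeds that of the pooled estimate at a true 5% (6.9 against 5.7 points) and at 20% (12.7 against 8.5). A result of 1/10 has an exact 95% interval of 0.3% to 44.5%, and 0/10 occurs with probability 0.95^10 = 60% at a true 5%. This stands as a reason to keep the pooled ORR primary. It is not a reason to leave out the one figure free of Stage 1 selection.

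**Conclusion.** The point holds as a modest improvement in reporting. For cells that pass the futility rule, the planned pooled ORR overstates the truth by about 3.7 points at a true 5% and 4.7 points at a true 1%, and by little at the rates the plan calls meaningful. These figures assume 10+10 participants, the same responses counted at the futility look and at the end, and expansion exactly when at least one response is seen.

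The 8.7% is the top of the scenarios worked here, which otherwise give about 6.1% to 8.0%. It is not a strict bound: holding back cells with a single response, or responses first appearing after the futility look, would push it up.

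Two stronger readings are tempting, and the documents do not support them.
- A reader might infer that every cell reaches Stage 2 only after a response of its own. Section 5.1.4 makes expansion permissive, brings in the totality of the data, and gives Arm B a route that needs no response in the cell itself.
- A reader might infer that the Clopper-Pearson interval fails in general among passing cells. The clear shortfall is confined to very low rates. At a true 1% only 9.6% of cells pass, so about 1.3% of such cells are affected.

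**What to change.** In Section 10.6.1, keep the pooled ORR and its Clopper-Pearson interval as primary. For each expanded cell, add the ORR and exact 95% interval from Stage 2 participants alone, labelled supportive. State that the pooled value is conditional on expansion, and record by which route in Section 5.1.4 the cell was expanded.

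The Stage 2-only figure is free of Stage 1 selection under every one of those routes, provided that the Stage 2 size is not changed in the light of its own results.

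A standard two-stage unbiased estimator (UMVUE) is not a substitute. It corrects the downward bias over all cells, and among passing cells its expected value at a true 5% is 12.5%, further from the truth than 8.7%.

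The cost is one table column and a sentence. The downside is a wide interval on about 10 participants per cell.

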### **10.6.2** Statistical Methods for Safety Analysis

Safety and tolerability will be assessed by clinical review of all relevant parameters including DLTs, AEs, SAEs, laboratory tests, vital signs, ECG measurements, and physical examinations

DLT and adverse events will be summarized by counts and frequencies for each arm. Laboratory tests, vital signs, and other safety endpoints will be summarized as appropriate (e.g., counts, percentages).

Miettinen and Nurminen's method will be used to estimate the difference between the 2 arms and its 95% confidence interval for number of participants with a DLT, number of participants with ≥1 AE and number of participants discontinuing study treatment due to an AE.

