### 7.3.1 Stratification

Treatment allocation/randomization will be stratified according to the following factors:

Tumor type (NSCLC [PD-(L)1 refractory], CRPC, and MSS CRC)

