Safety Analyses	as appropriate (e.g. counts, percentages). Miettinen and Nurminen's method will be used to estimate the difference			
	between the 2 arms and its 95% confidence interval for			
	number of participants with a DLT, number of participants			
	with ≥1 AE and number of participants discontinuing study			
Intorim Analysas	treatment due to an AE.  An interim safety analysis is planned for each arm after the			
Interim Analyses	An interim safety analysis is planned for each arm after the first 10 participants across tumor types have finished at least			
	one cycle of therapy in a given arm. An interim futility			
	analysis is planned for each tumor type in each arm after the			
	first 10 participants in each tumor type have finished the first tumor assessment.			
	Additional interim analysis may be conducted to enable			
	future trial planning at the Sponsor's discretion and data will			
	be examined on a continuous basis to allow for timely			
	decisions.			

89

**Product:** MK-7123 SCH 527123 **Protocol/Amendment No.:** 034-01

Multiplicity	No multiplicity adjustment is planned in this Phase 2 trial.	
Sample Size and Power	1 0 0	

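### The safety difference between dose arms names no tumor-type strata, although Stage 2 can leave the two arms with different tumor mixes (minor, nearly free to fix)

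*Combined protocol and SAP*

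**What the plan says.** Section 10.6.2 states that the Miettinen-Nurminen "method will be used to estimate the difference between the 2 arms and its 95% confidence interval" for three endpoints: DLT, at least one AE, and discontinuation due to an AE. The summary in section 10.1 says the same ("Nurminen's method will be used to estimate the difference"). Neither place mentions strata.

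Section 7.3.1 reads "Treatment allocation/randomization will be stratified according to the following factors" and lists one factor, tumor type. Under section 5.1, the futility analysis is done "to determine whether that tumor type and arm will progress to Stage 2". Section 5.1.4 says that after one or more responses "this tumor type may be expanded to enroll at least additional 10 participants in Stage 2". It adds one link between the arms: if a type is expanded in Arm A, "this tumor type in dose Arm B may be expanded to Stage 2 as well". That link is optional, and there is no matching rule from Arm B to Arm A.

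The introduction to section 10.6 says "This section describes the statistical methods that address the primary objectives" and "The final analyses will be performed using data from both Stage 1 and Stage 2". It also sends the comparison between arms to the sSAP in general terms. Section 10.10 commits to analysis by tumor type for efficacy only.

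**The concern.** Stage 1 gives each arm 10 participants per tumor type, so the mixes start equal. Stage 2 can break that balance: a type that passes only in Arm B opens only in Arm B, and a type that passes only in Arm A opens only there unless the optional carry-over is used. An unstratified difference then compares arms made up of different cancers. If toxicity or discontinuation rates differ by cancer, the estimate mixes a dose effect with a tumor-mix effect.

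Safety and tolerability is a primary objective, and this is the only between-arm difference whose method the SAP itself names. At stake is whether a reader comparing the two doses can tell how much of the point estimate comes from dose.

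**Working it through.** **1. The plan's own figure.** A type passes if at least 1 of 10 participants responds: q = 1 − (1 − p)^10. At 16%, q = 82.5%; at 20%, q = 89.3%. These agree with the 82% and 89% in section 10.7. At the uninteresting rates of section 10.9, taking 1% for the CRC figure, q = 9.6% at 1% and 40.1% at 5%.

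**2. How often the mixes differ.** Assumptions: the arms are independent with equal response rates, the rule is applied mechanically, and each open type adds 10 (20 per type, as planned in section 10.9). There are 2^6 = 64 pass/fail outcomes. If the carry-over is always used, a type differs only when it passes in B and fails in A, with probability q(1 − q).

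- Target rates, carry-over always used: 1 − (1 − 0.0958)²(1 − 0.1443) = 0.3005. Subtract 0.0013 for the case where all three types differ, which is 10/10/10 v 20/20/20 with equal shares. Result: 29.9%.
- The other cases follow in the same way:

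| Outcome | Carry-over always used | Never used |
|---|---|---|
| Mixes differ, ORR 20/20/16% | 29.9% | 53.3% |
| Mixes differ, ORR 5/5/1% | 46.8% | 76.7% |
| Matched 20/20/20 in both arms, ORR 20/20/16% | 66% | 43% |
| One type 20 v 10, others 20, ORR 20/20/16% | 26% | 39% |

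**3. Size of the shift with no dose effect.** Shift = event-rate gap × (share of the diverging type in one arm − its share in the other).

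- 20/20/20 v 10/20/20: 20/60 − 10/50 = 2/15. Gaps of 20 to 30 points give 2.7 to 4.0 points.
- 20/10/10 v 10/10/10: 20/40 − 10/30 = 1/6, giving 3.3 to 5.0 points.

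The documents give no event rates by tumor type, so the gaps are assumed. Rates of 30/10/10% and 40/10/10% were used, equal in both arms, with the diverging type as the high-rate type.

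Worked example at 30/10/10%: Arm B 20/10/10 has 6 + 1 + 1 = 8 of 40, and Arm A 10/10/10 has 3 + 1 + 1 = 5 of 30. Unstratified: 20.0% − 16.7% = +3.3 points (95% CI −16.5 to +21.5). Stratified with weights nA·nB/(nA + nB): 0.0 (−19.8 to +18.7).

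**4. Effect on the interval.** Miettinen-Nurminen score statistic at zero, 400,000 simulated trials per pattern:

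| Mix (one arm v the other) | Shift, points | 95% CI width, points | Zero excluded, unstratified | Zero excluded, stratified |
|---|---|---|---|---|
| 20/20/20 v 20/20/20 | 0 | – | 3.3–4.0% | about 4.9% |
| 20/20/20 v 10/20/20 | 2.7–4.0 | 28–30 | 5.8–6.9% | about 4.9% |
| 20/10/10 v 10/10/10 | 3.3–5.0 | 38–40 | 5.7–6.3% | about 4.9% |

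Averaged over all 64 outcomes, with each type in turn as the high-rate type, the unstratified interval excludes zero in 3.8–4.8% of trials at the target rates and 4.2–5.6% at 5/5/1%. The stratified interval does so in 4.9–5.0%. The mean absolute shift in mismatched trials is 1.8–3.2 points at the target rates and 1.7–4.0 points at 5/5/1%.

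**5. An extreme that the wording permits.** If all 30 Stage 2 places of one arm went to one type (40/10/10 v 10/10/10), the share difference is 2/3 − 1/3 = 1/3. The shift is then 6.7 to 10.0 points, and zero is excluded in 9.4–14.5% of trials. The at-least-10 wording allows this, but section 10.9 plans 20 per type.

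**6. What stratification leaves.** If event rates drift between stages, the stratified estimate keeps the split type's weight times its Stage 2 share in the open arm.

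- 20/20/20 v 10/20/20: 0.25 × 1/2 = 1/8 of the drift. Unstratified, for a drift shared by all types: 30/60 − 20/50 = 1/10.
- 20/10/10 v 10/10/10: 0.40 × 1/2 = 1/5. Unstratified: 10/40 − 0 = 1/4.

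For an assumed drift of 10 to 20 points, the stratified residue is 1.3–2.5 and 2.0–4.0 points.

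**The case against.** The strongest reply is that little depends on this interval. The stopping rules are DLT counts within each arm, the formal DLT review uses the first 10 evaluable participants per arm, and no formal hypothesis testing or multiplicity control is planned. The commonest outcome at the target rates is matched arms, where there is no bias and the unstratified interval is slightly conservative. All of that stands, and it is why the point is minor.

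The sSAP, which is not part of the documents, may add strata, and section 10.10 leaves room for further subgroup analyses there. That is possible. But section 10.6.1 expressly defers the efficacy comparison between arms, whereas section 10.6.2 fixes the safety method without such a pointer. One sentence would settle it.

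The event-rate gaps are assumed. This also stands: where rates are near 0% or 100% in every type, which could be so for rare DLTs or for having at least one AE, the shift is negligible. The chances in step 2 are mechanical, while actual expansion is discretionary and takes account of the totality of data.

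Finally, stratification does not remove drift between stages, and in the commonest mismatch it leaves slightly more of a shared drift (1/8 v 1/10). That is correct, and it is the reason to add a concurrent-only analysis.

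**Conclusion.** The concern holds as a minor point. Followed as written, the plan can report a dose difference in safety that includes a tumor-mix component, and it does not use the one factor by which the trial randomizes to remove it. In the ordinary mismatches the component is 2.7 to 5.0 points if event rates differ by 20 to 30 points between types and the diverging type is the high-rate one. That is small beside intervals 28 to 40 points wide, and it is zero when the mixes match. The benefit comes in a trial where the mixes do diverge: the reader can then see how much of the estimate is tumor mix. The case for the change rests mainly on its low cost.

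**What to change.** In sections 10.1 and 10.6.2, specify the Miettinen-Nurminen difference stratified by tumor type with sample-size weights, in the ASaT population (the DLT-evaluable population for DLTs). Summarize the safety endpoints by arm within tumor type. If a type opens in one arm only, also report the same difference restricted to participants randomized while both arms were open to their tumor type, because stratification does not restore concurrent randomization. If the sSAP already provides this, refer to it explicitly in section 10.6.2.

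The cost is two sentences and one table, some of whose cells will be small (10 participants per type and arm, with few DLTs). The stratum is already collected, and nobody is dropped from the main analysis. The stratified SD is 0.5–1.3% larger than the unstratified SD in the ordinary mismatches (9.1 v 9.0 points for 20/10/10 v 10/10/10), about 5% larger in the 40/10/10 case, and unchanged when the mixes match. The concurrent-only analysis adds a further 0.2–2.3% to the SD in the ordinary mismatches and needs the dates when each type was open in each arm.
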